14.2 PART 3: CHOLESTEROL SYNTHESIS

Study Subjects: 10 adolescents (as described above)

Study Design: Cholesterol synthesis will be measured in the fasting state (0 HR) and during the meal challenge (6 HR) before Gemcabene treatment begins (Week 0) and after treatment is complete (Week 12).

Sample Collection and Processing:

- (1) Plasma (250µL) will be collected at 0, and 6 HRS and frozen at -20 °C for deuterium enrichment analyses of free cholesterol (Metabolic Solutions, Inc.) by IRMS.
- (2) Plasma free cholesterol concentration

Data Analysis:

Deuterium enrichment in plasma free cholesterol and plasma water will be determined by IRMS. The fraction of newly synthesized cholesterol (DNC) will be calculated from body water and cholesterol deuterium enrichment using precursor-product relationships. Absolute cholesterol synthesis will be calculated as DNL (%) x plasma (free) cholesterol concentration.

Endpoints:

Primary Endpoint:

- Fractional cholesterol synthesis in the fasting state (0 HR) and during meal stimulation (6 HR)

Secondary Endpoint:

- Absolute cholesterol synthesis in the fasting state (0 HR) and during meal stimulation (6 HR)

Measurements for DNL and DNC endpoints:

| Measurement | 0 HR | 2 HR | 4 HR | 6 HR |
|--|------------------|------|------|------|
| Deuterium enrichment in VLDL-TG palmitate (1 mL of plasma to isolate VLDL-TG for IRMS analyses) | X (in duplicate) | x | x | x |
| Deuterium enrichment in plasma water (0.25 mL of plasma for IRMS or Cavity Ringdown Spectrometer analyses) | x | x | x | x |
| Deuterium enrichment in plasma free cholesterol (0.25 mL of plasma for IRMS analyses) | x | | | x |
| VLDL-TG palmitate concentration (GCMS) | x | | | x |
| Plasma free cholesterol concentration (Enzymatic Method) | x | | | x |

15 ADVERSE EVENT REPORTING

15.1 ADVERSE EVENTS AND SERIOUS ADVERSE EVENTS

15.1.1 DEFINITION OF ADVERSE EVENTS (AE)

Please refer to the main protocol.

15.1.2 DEFINITION OF SERIOUS ADVERSE EVENTS (SAE)

Please refer to the main protocol.

15.1.3 ADVERSE EVENT REPORTING

Please refer to the main protocol.

15.1.4 SERIOUS ADVERSE EVENT REPORTING

Please refer to the main protocol.

16 STATISTICAL CONSIDERATIONS

16.1 STATISTICAL ANALYSIS

Data will be examined to identify missing data from one or more timepoints. Paired-sample t-tests will be conducted for comparison between Baseline and Week 12, and p-values will be considered as significance when <0.05 . Missing data imputation methods will be used for the small number of missing data points ($<1\%$). If there is a clear linear pattern, the mean of the previous and subsequent data points will be used. If there is a lack of linear pattern over time, the average change plus the average mean of the outcome at its adjacent timepoints will be used to replace the missing data. For lipid and glucose metabolism variables, comparisons of the 6-hour response will be made using the incremental area under the curve (IAUC) using the trapezoidal method and paired analysis comparing individual timepoints at Baseline (0 hour, fasting) and post-prandially. Since the response variables will be measured repeatedly throughout the 6-hr period, the linear mixed model analysis will be utilized to compare the effects of the two different beverages, as well as the influence of sex. Specifically, a random intercept model will be assumed for each individual to incorporate the within-subject correlation with those random effects representing the influence of the repeated observations from the same subject.

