9.4.7 SUB-GROUP ANALYSES

The primary and secondary endpoints will be analyzed by sex and by presence or absence of select NAFLD genes which may alter response to the IP. Differences in the primary outcome (% change in ALT from Baseline to Week 12) will be compared among sexes and genetic subgroups using two-sample t-

tests or Wilcoxon rank sum tests, as applicable. Percent change for other continuous measures will be analyzed similarly. For subgroups with more than two levels, we will test for differences in percent change from baseline using analysis of variance (ANOVA) models with a Tukey-Kramer post-hoc multiple comparison procedure or a Kruskal Wallis test with a Dwass, Steel, Critchlow-Fligner multiple comparison procedure.

For raw changes in continuous measures (ALT, AST, etc.) subgroup analysis will be conducted using analysis of covariance (ANCOVA) models. Specifically, for each outcome of interest, we will compare the 12-week outcome measure between subgroups (e.g., sex) controlling for the baseline value of the outcome measure. Initial models will include the interaction between subgroup and baseline value to assess the homogeneity of slope assumption. If the assumption is met, the interaction will be removed and least square means with associated 95% confidence intervals will be provided for each subgroup. Differences in subgroup means will be reported and accompanied by 95% confidence intervals. If the assumption of homogeneity of slopes is violated, an alternative approach such as the Johnson-Neyman procedure, will be utilized.

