9.4.9 EXPLORATORY ANALYSES

Exploratory analyses are planned as described in the sub-study (appendix A).

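### Appendix A sub-study: the mixed model compares two beverages where one is given, absolute cholesterol synthesis uses the lipogenesis fraction, and the absolute DNL times do not match the palmitate schedule (minor)

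*Combined protocol and SAP*

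**What the plan says.** **Mixed model (16.1).** For responses measured repeatedly over the 6 hours, "the linear mixed model analysis will be utilized to compare the effects of the two different beverages, as well as the influence of sex". On the random part, "a random intercept model will be assumed for each individual". The same section also plans that "Paired-sample t-tests will be conducted for comparison between Baseline and Week 12", and that "comparisons of the 6-hour response will be made using the incremental area under the curve (IAUC) using the trapezoidal method".

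**What is given (12.1, 14).** Section 14 describes one fixed, fructose-enriched breakfast taken with a juice, the same at both visits. Section 12.1 states that the sub-study has no intervention beyond blood collection. The other drinks are plain water and the deuterated tracer.

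**Cholesterol formula (14.2).** The newly synthesized cholesterol fraction is named DNC and derived from body-water and cholesterol enrichment. The next sentence computes absolute cholesterol synthesis as the DNL percentage times plasma free cholesterol. Section 14.1 derives DNL from VLDL-TG palmitate enrichment. Section 12.1 labels the cholesterol endpoint DNC.

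**Absolute DNL (14.1, table in 14.2).** Absolute DNL is fractional DNL times VLDL-TG palmitate pool size and is a secondary endpoint at 0, 2, 4 and 6 h. The table marks palmitate concentration at 0 and 6 h. Palmitate and plasma-water enrichment are marked at all four times.

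**Status.** Section 9.4.9 treats the sub-study as exploratory. Section 3 lists post-prandial lipids and the rate of de novo lipogenesis among the trial's secondary endpoints.

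**The concern.** The sub-study exists to compare Week 12 with Baseline in the same participants. The one model that would use all the repeated samples is written for a beverage comparison that this design does not contain. An analyst must either drop the sentence or decide what was meant, possibly after seeing data.

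The cholesterol formula, programmed literally, would return a quantity driven by lipogenesis under the name of a cholesterol endpoint. The absolute DNL endpoint is promised at two times for which the table schedules no palmitate concentration, and nothing says how the pool is otherwise obtained.

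At stake are the mixed-model results and two sub-study secondary endpoints.

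**Working it through.** Appendix A states no sample-size or power figure for the sub-study, so there is no planned figure to reproduce. The check compares the sections and counts.

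**Inputs.** 10 participants (12.1, 13); 2 visits (14); 4 sampling times, 0, 2, 4 and 6 h (14). Planned rows per response: 10 × 2 × 4 = 80.

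**1. Mixed model**
- Beverage takes one value in all 80 rows. Intercept plus beverage has rank 1, so beverage adds 0 degrees of freedom. Adding sex gives rank 2, so a sex effect can still be fitted.
- With visit in place of beverage, the fixed part is intercept 1 + visit 1 + time 3 + visit × time 3 + sex 1 = 9 columns. The error degrees of freedom are:
  - participant: 10 − 2 = 8
  - participant-by-visit: 10 − 1 = 9
  - within visit: 80 − 20 − 3 − 3 = 54
- Total: 9 + 8 + 9 + 54 = 80, so the model can be estimated.
- The random intercept needs attention once visit is the contrast. Let σ² be the within-visit variance and τ² the participant-by-visit variance. The correct error mean square for visit is σ² + 4τ². A participant-only intercept pools the two inner strata: [9(σ² + 4τ²) + 54σ²] / 63 = σ² + (36/63)τ² = σ² + 0.57τ².
- The documents give no variances, so τ²/σ² is an assumption:

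| τ²/σ² (assumed) | pooled ÷ correct mean square | standard error ratio |
|---|---|---|
| 0 | 1 / 1 | 1.00 |
| 0.25 | 1.14 / 2 | 0.76 |
| 1 | 1.57 / 5 | 0.56 |

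- If visit × sex is added with 5 boys and 5 girls, the 95% CI half-width is t(0.975, 8) × √(2/5) = 2.306 × 0.632 = 1.46 SD of the participant change. A difference of 2.02 SD would be needed for 80% power.

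**2. Cholesterol formula**
- As written: DNL × free cholesterol. By the section's own definition: DNC × free cholesterol. The ratio is DNL/DNC, which equals 1 only if the two fractions coincide.
- The documents give values for neither fraction, so no numerical bias can be stated.
- With DNC, both inputs are scheduled at 0 and 6 h, the times at which this endpoint is due.

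**3. Absolute DNL**
- Due at {0, 2, 4, 6} h; palmitate concentration at {0, 6} h; unmatched at {2, 4} h.
- Unmatched values: 10 × 2 × 2 = 40 of 80 (50%).
- Whether these 40 lack an input depends on the meaning of pool size:
  - If it needs palmitate concentration at the same time, they cannot be calculated.
  - If it may be derived from VLDL triglyceride, they may be. Section 12.1 makes the incremental AUC of VLDL TG a primary endpoint, with samples at all four times.

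**The case against.** The strongest reply is that these are drafting slips in an exploratory sub-study of 10 and that the drug contrast is already specified. Much of that stands. The paired t-tests and incremental AUC in 16.1 compare Baseline with Week 12. Section 9.4.3 adds raw and percent change, with a t-test or Wilcoxon test, for all continuous secondary endpoints. Sex is covered in section 9.4.7: "The primary and secondary endpoints will be analyzed by sex". The sentence before the cholesterol formula defines DNC, so a careful analyst would probably use it.

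On absolute DNL, section 14.1 also lists palmitate concentration as a measurement without limiting its times, and pool size is left open. The conflict between the endpoint times and the table is real, but the formula itself is not shown to be wrong.

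A reader might also set the 40 unmatched values against the imputation rule in 16.1, which is meant for fewer than 1% of data points and under which, for a linear pattern, "the mean of the previous and subsequent data points will be used". That comparison is beside the point. The rule deals with scheduled values that go missing; these assays were never scheduled, and nothing proposes to impute them.

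What remains is that the beverage contrast cannot be estimated, the cholesterol formula names the wrong fraction, and pool size is undefined with endpoint times that do not match the table.

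**Conclusion.** Two analysis rules are wrong as written and one schedule conflicts with its endpoint. The importance is minor.

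- **Mixed model:** the beverage factor has one level and no visit term is named. Only this model is affected, including where it is applied to postprandial lipids and fractional DNL.
- **Cholesterol formula:** probably a slip; taken literally, it gives the wrong variable for a sub-study secondary endpoint.
- **Absolute DNL:** 40 of 80 values cannot be calculated if pool size requires same-time palmitate concentration, which is an assumption.

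Three stronger readings are not supported. The sub-study does not lose its test of gemcabene, because the paired analyses remain. Half of the absolute DNL data are not shown to be lost, because a pool derived from VLDL triglyceride is not excluded. No numerical bias in cholesterol synthesis is shown, because the documents give no fractions. The ALT endpoint, the sample size and the power are not affected.

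**What to change.** - **16.1:** replace the beverage comparison with Baseline against Week 12: fixed effects for visit, time, visit × time and sex, with a participant-by-visit random effect added to the participant intercept. The added term keeps the error of the visit contrast from being understated if participants differ in their change. Visit × sex is optional, as an estimate with 95% CI only; it largely repeats section 9.4.7 and is imprecise at 5 against 5. Keep the paired t-tests and incremental AUC.
- **14.2:** change DNL (%) to DNC (%) in the formula for absolute cholesterol synthesis.
- **14.1 and the table in 14.2:** define pool size, then reconcile the absolute DNL times with the measurement schedule. Restricting absolute DNL to 0 and 6 h needs no new assay.

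**Cost.** Appendix wording only, if absolute DNL is restricted. Keeping all four times through measured palmitate concentration would add 10 × 2 × 2 = 40 assays. The appendix gives several volumes (4 mL of plasma per time for fractionation, 1 mL for VLDL isolation, 0.25 mL each for the water and cholesterol enrichment assays) but not that of the palmitate concentration assay. The laboratory would have to confirm that the stored aliquots suffice. If pool size is instead defined from VLDL triglyceride, the cost is again wording.

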13 STUDY POPULATION

The sample for this study will include n=10 participants with NAFLD (~50% boys and ~50% girls) who are participating in the GEM-IIT-601 study. The sub-study will only be conducted at Emory. All Emory site participants will be invited to participate in the sub-study until 10 have been enrolled.

13.1 INCLUSION CRITERIA * *ADDITIONAL INCLUSION AND EXCLUSION CRITERIA (IN ADDITION TO THE MAIN STUDY CRITERIA)*

In order to be eligible to participate in this study, an individual must meet all of the following criteria:

- 10. Willing to participate in the sub-study and complete all sub-study procedures at Baseline and Week 12 visits
- 11. History of hypertriglyceridemia

13.2 EXCLUSION CRITERIA * *ADDITIONAL INCLUSION AND EXCLUSION CRITERIA (IN ADDITION TO THE MAIN STUDY CRITERIA)*

An individual who meets any of the following criteria will be excluded from participation in this study:

- 22. Food allergies including gluten sensitivities
- 23. Known reaction to deuterated water

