14 METHODS

After consent and assent to the main study, participants at Emory University will be informed of the sub-study at the Screening visit. Consent and assent for the sub-study will be obtained through providing details of the sub-study and procedures and through discussion. The postprandial lipid study will take place at the Baseline and Week 12 visit. Prior to the day of the visit, the participants will have a standardized meal provided for their evening meal. They will be asked not to consume any sugar

containing beverages including juice. The meal will be identical at Baseline and Week 12 and will consist of a commercially prepared frozen dinner that can be microwaved at the time of consumption. It will be shipped frozen to the participant's home along with instructions.

Deuterated water: De novo lipogenesis and cholesterol synthesis can be studied by measuring the incorporation of deuterium from deuterated water into VLDL-TG palmitate and plasma free cholesterol. Two 60 ml bottles of deuterated water (D, 70%) will be provided the evening prior to the DNL and DNC assessments. One bottle will be consumed with the standardized evening meal and one bottle 3 hours later around bedtime.

No food or flavored drinks will be allowed after 7 pm the day prior to the visit to ensure 8 hours of fasting. Participants will be asked to consume one glass of water in the morning prior to driving to the research center to ensure good hydration at the time of the sub-study.

On the morning of the visit, at the pediatric research unit, participants will have an IV placed during the initial blood draw to make repeated blood draws more comfortable. After fasting labs are completed, a standardized breakfast will be provided (approximately 30% fat [~12% polyunsaturated, 8% saturated, and 10% monounsaturated], 15% protein and 55% carbohydrates consumed in combination with a juice beverage). The standardized breakfast will be enriched with fructose to stimulate DNL and will be identical at Baseline (Week 0) and Week 12 assessments. It will be a fixed meal and not calorie-adjusted for body weight.

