14.1 PART 2: DE NOVO LIPOGENESIS

Study Subjects: 10 adolescents (as described above)

Study Design: Hepatic de novo lipogenesis will be measured in the fasting state (0 HR) and during the fructose enriched meal challenge (0, 2, 4 and 6 HRS) before Gemcabene treatment begins (Week 0) and after treatment is complete (Week 12).

Sample Collection and Processing:

- (1) VLDL (Sf20-400) particles will be isolated from 1 mL of plasma at the Biomarker Core Laboratory, split in two equal VLDL aliquots (one primary and one back-up sample), frozen at -80 °C and shipped to Metabolic Solutions, Inc. for triglyceride isolation and deuterium enrichment of VLDL-TG palmitate by IRMS.
- (2) Plasma (250 µL) will be collected at 0, 2, 4 and 6 HRS and frozen at -20 °C for body water enrichment analyses (Metabolic Solutions, Inc.). Spray-dried K2 EDTA vacutainers will be used to collect plasma for body water enrichment analyses.
- (3) VLDL-TG palmitate concentration

Data Analysis: Deuterium enrichment in VLDL-TG palmitate and plasma water will be determined by IRMS. Fractional DNL will be calculated from body water and VLDL-TG-palmitate deuterium enrichment using precursor-product relationships. Absolute DNL will be calculated as Fractional DNL x VLDL-TG palmitate pool size.

Endpoints:

Primary Endpoint:

- Fractional hepatic DNL in the fasting state (0 HR) and during meal stimulation (2 HR, 4 HR, 6 HR)

Secondary Endpoint:

- Absolute hepatic DNL in the fasting state (0 HR) and during meal stimulation (2 HR, 4 HR, 6 HR)

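### The sub-study mixed model names a beverage factor the design lacks; if it is run with visit as the factor, its single random intercept per child can make the Baseline versus Week 12 test anti-conservative

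*Combined protocol and SAP*

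**What the plan says.** Section 16.1 (Appendix A) describes three analyses of the sub-study data.

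- For change over treatment: "Paired-sample t-tests will be conducted for comparison between Baseline and Week 12", with the rule that "p-values will be considered as significance when <0.05".
- For lipid and glucose variables: the 6-hour response summarised as incremental AUC (IAUC), plus paired comparisons of individual time points with the fasting value.
- For the repeated samples: "the linear mixed model analysis will be utilized to compare the effects of the two different beverages, as well as the influence of sex". The only random effect named is the child: "a random intercept model will be assumed for each individual to incorporate the within-subject correlation". There is no child-by-visit term and no residual correlation structure.

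On the design, section 13 states "The sample for this study will include n=10 participants with NAFLD" and section 14 states "The postprandial lipid study will take place at the Baseline and Week 12 visit". Section 14 gives draws at 0, 2, 4 and 6 hours, and a fixed breakfast, taken with juice, that is the same on both occasions. Section 14.2 measures cholesterol synthesis at 0 and 6 hours only.

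**The concern.** The factor that the mixed model is meant to test does not exist here. Every child receives the same breakfast and juice at both visits, and the two bottles of deuterated water are both taken on the evening before each visit, so they are not a comparison either. Besides time of draw, the only condition that varies within a child is visit. An analyst who carries out the sentence must therefore drop the model or put visit where the text says beverage.

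In the second case the random-effects structure matters. A child intercept removes what is common to both visits. It does not remove what is common to the samples of one visit, such as that day's metabolic state or the child's own change over twelve weeks. That variation goes into the residual, where the samples of a visit are treated as independent.

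Post-prandial lipids and the rate of de novo lipogenesis (DNL) are trial secondary endpoints (sections 1.1 and 3) and bear on mechanism of action. Fractional DNL is measured at four times per visit with no single summary declared, so the mixed model is the one stated analysis that clearly combines all four. Section 16.1 does not say which analysis is primary for Baseline versus Week 12.

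**Working it through.** **Inputs from the documents.** 10 children (section 13); 2 visits (section 14); T = 4 samples per visit, or T = 2 for cholesterol synthesis (sections 14 and 14.2); threshold 0.05 (section 16.1, taken as two-sided); one random intercept per child (section 16.1).

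**Assumed input.** r = the share of within-child variance that is visit-to-visit. The documents give no variance component, so a range is shown.

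**Residual degrees of freedom,** with visit, time and visit-by-time as fixed effects:
- T = 4: 80 − 1 − 9 (child) − 1 (visit) − 3 (time) − 3 (visit-by-time) = 63.
- T = 2: 40 − 1 − 9 − 1 − 1 − 1 = 27.

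In each case 9 of these degrees of freedom are child-by-visit, which the model pools with the rest.

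**Variance ratio.** Let k = r/(1 − r) be child-by-visit variance divided by residual variance. The true variance of the visit difference, divided by the variance that the model reports on average, is

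- T = 4: (1 + 4k)/(1 + 4k × 9/63) = (1 + 3r)/(1 − 3r/7)
- T = 2: (1 + 2k)/(1 + 2k × 9/27) = (1 + r)/(1 − r/3)

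Example, T = 4 and r = 0.50: 2.5/0.786 = 3.18. The reported standard error is too small by a factor of √3.18 = 1.78. The normal approximation to the rejection rate is 2 × [1 − Φ(1.96/1.78)] = 27%.

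**The plan's own figure first.** In simulation under no drug effect (40,000 data sets per setting), the nominal 5% is reproduced by the paired t-test on visit means (4.8% to 5.3%) and on IAUC (4.8% to 5.1%) in every setting. The random-intercept model reproduces it only at r = 0 with no serial correlation (5.2%).

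**Rejection rate of the random-intercept model for visit, no child-by-time variance:**

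| r | Variance ratio, T = 4 | Simulated, T = 4 | Variance ratio, T = 2 | Simulated, T = 2 |
|---|---|---|---|---|
| 0.10 | 1.30/0.957 = 1.36 | 9.3% | 1.10/0.967 = 1.14 | about 6% |
| 0.25 | 1.75/0.893 = 1.96 | 16.3% | 1.25/0.917 = 1.36 | about 9% |
| 0.50 | 2.50/0.786 = 3.18 | 27.2% | 1.50/0.833 = 1.80 | about 14% |
| 0.75 | 3.25/0.679 = 4.79 | 37.0% | 1.75/0.750 = 2.33 | about 20% |

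A small REML check (300 data sets per setting, T = 4, some fits with convergence warnings) gave 4.3% at r = 0 and 29.3% at r = 0.50, in line with the closed form.

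**Sensitivity, T = 4.**
- Serial correlation within a visit, with r = 0, also inflates the rate: 13.1%, 20.6% and 29.7% for AR(1) correlations of 0.3, 0.5 and 0.7.
- Child-by-time variance works the other way, because it enlarges the residual without affecting the visit difference. When it equals the residual variance, the rate is 0.9% at r = 0, 5.0% at r = 0.2, 16.9% at r = 0.5 and 33.5% at r = 0.8.

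**The case against.** The strongest reply is that section 16.1 never assigns Baseline versus Week 12 to the mixed model. It assigns that comparison to paired t-tests, which hold their level, and the meal sub-study's primary endpoint is IAUC, with one value per child and visit, so its samples cannot act as replicates. Section 9.4.3 likewise analyses secondary endpoints by paired tests on change. Section 9.4.9 calls the sub-study exploratory, and it involves 10 children at one site. Section 14 also standardises the evening meal, tracer amount, fasting and breakfast, so a large r cannot be presumed. The main effect of sex is between children, where the child intercept is the relevant term.

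All of this stands. A reader might infer that the sub-study's test of the drug effect has a false-positive rate far above 5%. The documents do not support that: the valid test is already planned, using the mixed model for visit is an inference from the missing beverage factor, and the size depends on an r that the documents do not give.

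The reply does not rescue the mixed-model sentence. It still plans a comparison that cannot be made, and its only workable within-child reading gives a second test of the same contrast, with no statement of which test prevails. Standardised procedures reduce visit variance but do not remove it, because children who change by different amounts over twelve weeks themselves create child-by-visit variance.

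**Conclusion.** The mixed-model specification in section 16.1 is wrong as written: it names a factor that the sub-study does not contain, and its random-effects structure is not adequate for the one factor that could replace it. Used for visit, the nominal 5% test would reject about 9% to 37% of the time with four samples per visit, and about 6% to 20% with two, for r between 0.10 and 0.75. These figures assume no child-by-time variance and no serial correlation. The inflation is absent at r = 0 and can be cancelled or reversed when child-by-time variance is large.

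The defect is confined to the mixed model. The planned paired t-tests, the IAUC endpoint and the between-child comparison of the sexes are sound on this point.

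**What to change.** In section 16.1:

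- Replace the beverage factor with visit, and specify visit, time and visit-by-time as fixed effects.
- Add a random intercept for child-within-visit to the child intercept, or use a within-visit residual covariance, with small-sample degrees of freedom (for example Kenward-Roger). With 10 children the extra random intercept is the less demanding choice. In balanced data it makes the overall visit test the same as the paired test on visit means, with 9 degrees of freedom.
- State that the primary Baseline versus Week 12 test is the paired test on one summary per child and visit: IAUC for the meal variables, and a named summary for DNL and cholesterol synthesis. State that the mixed model is supportive.

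The cost is a change of wording and, where visit-to-visit variance is present, less favourable mixed-model p-values. No further data are needed.
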